5 CRITERIA FOR EVALUATION

5.1 Primary Safety Endpoint

Safety will be measured by the frequency and grade of solicited and unsolicited adverse events (AEs), SAEs, AESIs and MAAEs. Reactogenicity will be measured by the occurrence of solicited injection site and systemic reactions.

1. Frequency and grade of each solicited local and systemic reactogenicity AE will be recorded on a daily diary using the FDA Toxicity Grading Scale and collected from Day 1 until Day 7.
2. Frequency and grade of each unsolicited AEs will be recorded on a daily diary and collected from Day 1 until Day 30.
3. Frequency of any SAEs, AESIs and MAAEs will be collected from Day 1 until Day 180.

Simple descriptive statistics will be used to summarize toxicities in terms of type, severity and minimum or maximum values for laboratory measures, time of onset, duration, and reversibility or outcome. Tables will be created to summarize these toxicities and side effects. Safety Analyses will be performed on the Safety Analysis Set.

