Lung transplant recipients, due to their immune suppression medicines, have had weak responses to the COVID-19 vaccines with antibody responses noted in less than 20% after the second vaccine dose (16–18). Lung transplantation is also unique among the solid organ transplants in the direct infection and injury of the allograft by SARS-CoV-2. Thus, lung transplant recipients have poor outcomes following COVID-19 infection with a high mortality rate. Third dose vaccines appear to improve immune responses for solid organ recipients, but has not been studied specifically for lung transplant recipients.

The current CDC guidance is for moderately or severely immunocompromised patients to receive a 50 ug booster: 1) At least 3 months after 3rd dose (first booster), and 2) At least 4 months after 4th dose (2nd booster). We believe that this dosing will be insufficient for many lung transplant recipients, particularly in those who did not receive any vaccine doses prior to their lung transplant, and leave them at high risk of poor COVID-19 outcomes. Importantly, due to their immunosuppression, lung recipients appear to have decreased side effects and reactogenicity to the SARS-CoV-2 vaccine.

We hypothesize that a 100 ug mid-dose and 200 ug high-dose mRNA-1273 booster dose can be safely administered to lung transplant recipients who previously received all of their vaccine doses after their lung transplant. We further hypothesize that the higher dose boosters will induce a stronger immune response to SARS-CoV-2 as measured by humoral and cellular response assays. The objectives of this study are to test these two hypotheses.

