6.2 Inclusion Criteria

1. All adult lung transplant recipients (age ≥ 18 at the time of consent) who received all of their COVID-19 vaccines after lung transplantation.
2. Received three or four doses of either the Moderna mRNA-1273 or Pfizer BNT162b2 vaccine with the last dose received at least 4 months prior to study enrollment.
3. Currently receiving standard regimen of three drug immunosuppression with prednisone, tacrolimus and mycophenolate mofetil (minimum 250 mg bid) or mycophenolate sodium (minimum 180 mg bid).

4. Agrees not to receive other investigational agents for prophylaxis against COVID-19 including Evusheld monoclonal antibodies for at least 30 days after the study vaccine.
5. Understands and agrees to comply with the study procedures and provides written informed consent.
6. Is in stable health without any new or worsening medical conditions in the opinion of the Investigator.
7. Female participants of childbearing potential (<1 year since start of menopause) may be enrolled in the study if the participant fulfills all the following criteria:
 - a. Has a negative pregnancy test at Visit 1 Day 1.
 - b. Has practiced adequate contraception or has abstained from all activities that could result in pregnancy for at least 28 days prior to the first injection (Day 1).
 - c. Has agreed to continue adequate contraception or practice abstinence through 3 months following the booster injection (Day 90).
 - d. Is not currently breastfeeding.
 - e. Adequate female contraception is defined as consistent and correct use of a Food and Drug Administration (FDA) approved contraceptive method in accordance with the product label. For example:
 - i. Barrier method (such as condoms, diaphragm, or cervical cap) used in conjunction with spermicide
 - ii. Intrauterine device
 - iii. Prescription hormonal contraceptive taken or administered via oral (pill), transdermal (patch), subdermal, or IM route
 - iv. Sterilization of a female participant's monogamous male partner prior to entry into the study
 - v. Note: periodic abstinence (e.g., calendar, ovulation methods) and withdrawal are not acceptable methods of contraception.

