7.2 Prohibited Medications and Treatments

Use of investigational agents for prophylaxis against COVID-19 within 90 days of the start of the study, including Evusheld monoclonal antibodies. Use of investigational agents for prophylaxis including Evusheld against COVID-19 for at least 30 days after study vaccination, since this will affect the antibody-based secondary endpoints.

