10.2 Visit 1 Day 1 (Clinic): Booster Vaccine Day

1. For participants who meet inclusion/exclusion criteria, the investigator team will again review the study with the participant (or participant's legal representative) in person and obtain written informed consent and HIPAA authorization.
2. Record demographic data.
3. Record medical history.
4. Review of birth control history with female participants of childbearing potential (<1 year since start of menopause).

5. For women of childbearing potential, counsel participants to use adequate birth control methods required during the trial to avoid pregnancy.
6. For women of childbearing potential, urine pregnancy test will be checked prior to study drug administration on Visit 1 (Day 1).
7. Confirmation participants meet all inclusion criteria and no exclusion criteria review.
8. Review pre-study concomitant medications and therapies and record on the appropriate CRF.
9. Review of influenza and any all 2019-CoV vaccinations or other experimental coronavirus vaccines.
10. Vital signs (HR, BP, temperature, oximetry), and height and weight for determination of BMI.
11. Full physical exam will include assessments of the following organs and organ systems: skin, head, ears, eyes, nose, and throat (HEENT), neck, lungs, heart, liver, spleen, abdomen, extremities, lymph nodes (axillary and cervical), and nervous system.
12. Obtain blood samples for baseline: Total immunoglobulins (IgG, IgA, IgM), anti-RBD, anti-spike binding and neutralizing antibody levels, PBMCs collected for cellular response assays including flow cytometry with intracellular staining, whole blood collected for cellular response assays, troponin / CK and cytokines for storage.
13. Confirm group assignment: standard-dose, mid-dose or high-dose group.
14. Inform participants of their designated dose.
15. Administration of booster vaccine.
16. Participants will be observed for 30-minutes post injection administration.
17. Dispense daily diary of symptoms for first 7 days after injection dispensed to participant measuring FDA Toxicity Grading Scale and adverse events.

10.3 Visit 2 Day 3 +/-1 Day (Phone – 2 days post booster):

1. All participants will complete a daily diary of solicited and unsolicited AEs from the vaccination until 7 days post-vaccination. Reactogenicity will be measured by the occurrence of solicited injection site and systemic reactions for the first 7 days post-vaccination utilizing the FDA Toxicity Grading Scale.

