14.6 Sample Size Justification

The overall mean \log_{10} IgG increase after the third (100 ug) vaccine dose was 0.46 with standard deviation (SD) 0.63. Assuming participants have a 50% lower response to the 50 ug fourth-dose, the expected mean \log_{10} IgG increase is 0.23. Assuming participants have a 100% higher response to the 200 ug fourth-dose, their expected mean \log_{10} IgG increase is 0.91. For 80% power to detect this difference between high-dose and standard-dose groups with a SD of 0.63 for a two-sample t-test with two-sided $\alpha<0.05$ significance, the minimum required sample size is 15 per group. Thus, we will enroll 20 participants in each group. The first 2 participants in the mid and high-dose groups will be enrolled as the sentinel group to ensure an acceptable safety profile before the full group is enrolled.

If the halting criteria is triggered for the high-dose group and further enrollment of this group is not recommended by the study investigators, DSMB or IRB, the study will continue randomized enrollment into the mid-dose and standard-dose groups with a 1:2 ratio to complete the enrollment of 60 participants total. Since the expected immunogenicity difference between the mid-dose and standard-dose group is smaller, we will require more participants to detect a difference between these two groups. The 1:2 enrollment ratio into the mid-dose and standard-dose groups will even the distribution of participants into these two groups. The primary endpoint analysis for safety and reactogenicity will not be affected by a restriction of participants into the mid-dose and standard-dose groups.

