APPENDIX 1. SCHEDULE OF EVENTS

	Screening Day -30 to Day 0	Visit 1 Day 1 Clinic	Visit 2 Day 3 Phone +/-1 day	Visit 3 Day 7 Clinic +/-2 days	Visit 4 Day 30 Clinic +/-7 days	Visit 5 Day 90 Phone +/-7 days	Visit 6 Day 180 Phone +/-7 days	Unscheduled visit as needed
Informed Consent		X						
Demographic data		X						
Medical History		X						
Eligibility review	X	X						
Con meds		X						
Pre-study meds		X						
Review CoV vaccinations		X						
Height		X						
Weight		X		X	X			
Vital Signs (HR, BP, temperature, oximetry)		X		X	X			
Full physical exam		X						X

Phase I/II, Open-label Dose-finding Trial of High-Dose mRNA-1273 Booster for Lung Transplant Recipients
Confidential

Targeted physical exam				X	X			
Blood draw*		X		X	X			X
Group assignment		X						
IP administration		X						
30-minute post-dose observation		X						
Review AEs, SAEs, AESIs, MAAEs			X	X	X	X	X	X
Review myocarditis and pericarditis symptoms			X	X	X	X	X	X
Dispense daily diary		X						
Diary review			X	X				
Pregnancy test (women of child-bearing potential)		X						
Birth control history (women of child-bearing potential)		X						
Review participants' use of appropriate birth control (if applicable)		X						

*Baseline labs must be drawn before vaccine dose. Day 7 must be drawn +/- 2 days. All other labs can be drawn +/- 7 days.

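### Non-study COVID-19 vaccine doses after Day 1 are neither limited nor scheduled to be recorded, so late SAEs, AESIs and MAAEs cannot reliably be separated from a second vaccine exposure

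*Combined protocol and SAP*

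**What the plan says.** The third part of the primary endpoint in section 5.1 reads: "Frequency of any SAEs, AESIs and MAAEs will be collected from Day 1 until Day 180". Section 14.1 assigns safety data to the treatment actually received. Sections 14.3 and 14.5 summarise them descriptively, with no rule for events that follow a vaccine given outside the study.

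Entry requires: "Received three or four doses of either the Moderna mRNA-1273 or Pfizer BNT162b2 vaccine with the last dose received at least 4 months prior" (section 6.2). The study injection is therefore a fourth or fifth dose. The guidance cited in section 2.1 places the next booster "At least 4 months after 4th dose (2nd booster".

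On restrictions after dosing, section 7.2 lists: "Use of investigational agents for prophylaxis including Evusheld against COVID-19 for at least 30 days after study vaccination". Section 6.2 asks participants to agree to the same limit. Neither names authorised vaccines.

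On recording, section 10.2 schedules this at Visit 1: "Review of influenza and any all 2019-CoV vaccinations or other experimental coronavirus vaccines". In Appendix 1 the row "Review CoV vaccinations" has a single mark, at Visit 1, and so does the concomitant medication row. Sections 10.6 and 10.7 limit the Day 90 and Day 180 calls to adverse events. Section 10.2 also instructs staff: "Inform participants of their designated dose".

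**The concern.** A late event is credited to the study dose whether or not another COVID-19 vaccine came in between. MAAEs are the class most open to this, because section 11.1 defines them to include an unscheduled medical visit whatever the reason. A visit prompted by a reaction to a later booster would count against the study dose.

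The schedule never collects the date of a non-study vaccine. After database lock the analyst could neither reliably separate such events nor say how many participants in each dose group had been re-vaccinated. Dates not collected during follow-up may be hard to recover. The component affected is part of the primary endpoint.

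**Working it through.** No planned figure needs reproducing. The check compares the relevant sections and then does date arithmetic.

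**1. Is an authorised booster limited?** Sections 6.2 and 7.2 cover investigational prophylaxis for at least 30 days after the study vaccine. Section 7 allows other investigational COVID-19 drugs after Day 45. Neither addresses authorised vaccines.

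**2. Is one recorded?** Vaccine review is at Visit 1 only (section 10.2, Appendix 1). Sections 10.3 to 10.8 list adverse-event review and no vaccine update.

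**3. When could one occur?** For participants with three prior doses the study injection is the fourth. The sample-size text in section 14.6 uses the same description: "Assuming participants have a 50% lower response to the 50 ug fourth-dose". Count the injection as Day 1 and add four calendar months.
- Four calendar months are 120 to 123 days, depending on the start date, so eligibility begins at Day 121 to Day 124.
- Days left to Day 180, counting both ends: 180 − 121 + 1 = 60, and 180 − 124 + 1 = 57.
- Share of the window: 60/180 = 33.3%, and 57/180 = 31.7%.
- With the final call at Day 173 the remainder is 53 to 50 days. At Day 187 it is 67 to 64 days.

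Eligibility therefore begins between the Day 90 call (latest Day 97) and the Day 180 call (earliest Day 173), with no scheduled contact in between. For participants with four prior doses, the cited guidance names no further booster.

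**4. Which endpoints can a guidance-timed dose reach?**
- Solicited reactions end at Day 7 and unsolicited events at Day 30: not reached.
- Immunogenicity is measured at Day 30, latest Day 37: not reached.
- The halting windows in 12.2 and 12.3 run at most 90 days: not reached.
- SAEs, AESIs and MAAEs to Day 180: reached from about Day 121.

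**5. How many participants?** Number re-vaccinated = (number with three prior doses) × (uptake). The first factor can be anything from 0 to 60 and the second anything from 0 to 1, so the product lies between 0 and 60. The documents do not narrow this. With 20 per group, one participant with a wrongly credited event moves that group's rate by 1/20 = 5 percentage points.

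For scale, section 1.2 gives 3.5 myocarditis/pericarditis cases per million second doses among all adults. If all 60 participants took an extra dose, that rate implies 60 × 3.5/1,000,000 = 0.00021 cases. It comes from a different population and dose number, so it shows only an order of magnitude. MAAEs are the realistic route for misattribution.

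**The case against.** The plan has partial safeguards. Section 11.1 requires the onset date, the relationship to study product and any other possible cause for each adverse event, and section 11.3 requires a narrative for each AESI. A recent booster is an obvious entry in either place. This stands, but it is unprompted and works only if the investigator learns of the other dose. It also covers only participants who have an event, so it cannot show re-vaccination by group.

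The reach is narrow. Four months is a minimum interval, so Day 121 is earliest eligibility and not a due date, and one third of the window is an upper bound. After Day 30 an ordinary reaction counts only if it is an SAE, AESI or MAAE. The analysis is descriptive, with no between-group test. All of this stands and limits the point.

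Three stronger readings are tempting but unsupported:
- A reader might infer that participants told they received 50 ug would seek extra doses more often, inflating the comparator and hiding a dose-related excess. Open-label dosing makes this possible, but no section speaks to booster-seeking by group. Stratification by number of prior doses should balance eligibility within each randomised cohort; it does not control uptake.
- A reader might put a count on it. Taking 30 of 60 participants and 20% to 80% uptake gives 30 × 0.2 = 6 to 30 × 0.8 = 24, but both inputs are assumptions.
- A reader might infer that Day 30 immunogenicity is at risk. A dose before that draw would fall outside the cited guidance intervals. The list of violations in section 13 is open-ended, so such a dose cannot be said to escape it, although the per-protocol definition in 14.1 does not mention it.

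**Conclusion.** The gap is real and limited, and closing it is a cheap improvement. Authorised non-study COVID-19 vaccines after Day 1 are neither restricted nor scheduled to be recorded. For participants with three prior doses, up to 57 to 60 days, at most about one third of the Day 1 to 180 window, could follow a second vaccine exposure. The existing adverse-event items do not close the gap.

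The conclusion assumes that the study injection counts as the fourth dose under the cited guidance, that some three-dose participants are enrolled, and that section 11.4, whose text was not available to check, adds no vaccine update. The number re-vaccinated, the number of misattributed events and any direction of bias between groups cannot be derived from the documents and are not claimed.

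**What to change.** - **Sections 10.5 to 10.8 and Appendix 1:** mark "Review CoV vaccinations" at Visits 4 to 6 and at unscheduled visits, and record the product and date of any non-study COVID-19 vaccine.
- **Section 14.3:** keep the full Day 1 to 180 table as primary. Report the number re-vaccinated by dose group. Add a supplementary table of SAEs, AESIs and MAAEs before and after the first non-study vaccine, with person-time denominators, because plain frequencies cut at that date would compare unequal follow-up.
- **Section 14.4:** list any non-study vaccine given before the Day 30 draw and handle it in a sensitivity analysis. Dropping such participants from the main analysis would condition on a choice made after randomisation and with the dose known.

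The cost is one question at contacts that already take place, one CRF field and one extra table. In the supplementary table the time at risk is shorter and may differ between dose groups, so it should be read as supportive only. No change to care or to access to vaccination is proposed.

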5.2 Secondary Immunogenicity Endpoints

1. **Binding antibody:** The anti-RBD and anti-spike (S-2P) IgG concentrations (log10 and geometric mean concentrations (GMC)) at Day 30 will be evaluated with comparisons between the standard-dose versus high-dose groups. T-tests with two-sided $p<0.05$ significance will be used (overall α level of 0.1). Changes in the anti-RBC and anti-spike IgG concentrations at Day 30 will be compared pairwise between the standard-dose versus high-dose groups using two sample T-tests with two-sided $p<0.05$ significance (overall α level of 0.1). The percent of participants with detectable antibody levels (greater than the LLOQ) at Day 30 will also be evaluated using Fisher's exact tests. Pairwise comparisons of binding antibodies will also be evaluated between the standard-dose versus mid-dose groups.
2. **Neutralizing antibody:** Neutralizing antibody titers (geometric mean titers (GMT)) from a pseudovirus neutralization assay at Day 30 will be compared between the standard-dose versus high-dose groups using T-tests with two-sided $p<0.05$ significance (overall α level of 0.1). Changes in the neutralizing antibody titers at Day 30 will be compared between the standard-dose versus high-dose groups using two sample T-tests with two-sided $p<0.05$ significance (overall α level of 0.1). The percent of participants with detectable neutralizing antibody levels (greater than the LLOQ) at Day 30 will also be evaluated using Fisher's exact tests. Pairwise comparisons of neutralizing antibodies will also be evaluated between the standard-dose versus mid-dose groups.
3. **Cellular immunogenicity:** The change in the frequency of target cytokine producing T-cells by flow cytometry with intracellular staining at Day 30 will be compared using the Kruskal-Wallis Test for standard-dose versus high-dose groups. A comparison of T-cell frequencies between the standard-dose versus high-dose groups will be evaluated using the Wilcoxon rank-sum test. Pairwise comparisons of cellular immunogenicity will also be evaluated between the standard-dose versus mid-dose groups.

5.3 Safety Evaluations

The study will use a Data and Safety Monitoring Board (DSMB). DSMB reviews are required for study halting and restarting. Reporting to regulatory bodies (IRB, FDA) will only be required for serious adverse events judged by the treating physician and study investigators to be potentially related to the administration of the study drug, including suspected, unexpected, serious adverse reactions (SUSAR, Section 11). All other adverse events will be reviewed by the study investigators and reported per FDA and IRB regulations. The study will be overseen by CTSI Data and Safety monitoring Board. By allowing CTSI DSMB to oversee the study, the PI agrees to abide by the CTSI DSMB's policies and procedures as outlined in the DSMB charter.

Safety evaluations:

1. **Visit 1:** Day 1 (booster day): informed consent, med history, inclusion criteria review, physical exam, blood draw, administration of booster, 30-minute observation.
2. **Telephone visit Day 3:** Review for AEs, SAEs, AESIs and MAAEs.
3. **Visit 2:** Day 7 - blood draw, physical exam and review for AEs, SAEs, AESIs and MAAEs.
4. **Visit 3:** Day 30 - blood draw, physical exam and review for AEs, SAEs, AESIs and MAAEs.
5. **Telephone visit Day 90:** Review for AEs, SAEs, AESIs and MAAEs.
6. **Telephone visit Day 180:** Review for AEs, SAEs, AESIs and MAAEs.

The following labs will be collected at baseline and clinic follow-up visits.

1. Serum collected for antibody levels.
2. PBMCs collected for cellular response assays including flow cytometry with intracellular staining.
3. Whole blood collected for cellular response assays.
4. Troponin, CK and cytokines banked from Day 0, 7 and 30.

6 PARTICIPANT SELECTION

6.1 Study Population

Participants post lung transplant who previously received three or four mRNA-1273 or BNT162b2 COVID-19 vaccines who meet the inclusion and exclusion criteria will be eligible for participation in this study.

6.2 Inclusion Criteria

1. All adult lung transplant recipients (age ≥ 18 at the time of consent) who received all of their COVID-19 vaccines after lung transplantation.
2. Received three or four doses of either the Moderna mRNA-1273 or Pfizer BNT162b2 vaccine with the last dose received at least 4 months prior to study enrollment.
3. Currently receiving standard regimen of three drug immunosuppression with prednisone, tacrolimus and mycophenolate mofetil (minimum 250 mg bid) or mycophenolate sodium (minimum 180 mg bid).

4. Agrees not to receive other investigational agents for prophylaxis against COVID-19 including Evusheld monoclonal antibodies for at least 30 days after the study vaccine.
5. Understands and agrees to comply with the study procedures and provides written informed consent.
6. Is in stable health without any new or worsening medical conditions in the opinion of the Investigator.
7. Female participants of childbearing potential (<1 year since start of menopause) may be enrolled in the study if the participant fulfills all the following criteria:
 - a. Has a negative pregnancy test at Visit 1 Day 1.
 - b. Has practiced adequate contraception or has abstained from all activities that could result in pregnancy for at least 28 days prior to the first injection (Day 1).
 - c. Has agreed to continue adequate contraception or practice abstinence through 3 months following the booster injection (Day 90).
 - d. Is not currently breastfeeding.
 - e. Adequate female contraception is defined as consistent and correct use of a Food and Drug Administration (FDA) approved contraceptive method in accordance with the product label. For example:
 - i. Barrier method (such as condoms, diaphragm, or cervical cap) used in conjunction with spermicide
 - ii. Intrauterine device
 - iii. Prescription hormonal contraceptive taken or administered via oral (pill), transdermal (patch), subdermal, or IM route
 - iv. Sterilization of a female participant's monogamous male partner prior to entry into the study
 - v. Note: periodic abstinence (e.g., calendar, ovulation methods) and withdrawal are not acceptable methods of contraception.

